#### 4.9.3. **Tumor Biopsy**

Fresh tumor biopsies (defined as a biopsy specimen taken since completion of the most recent prior chemotherapy regimen) will be required at baseline and on treatment of the same lesion (day 42  $\pm$  5 days). Patients are not required to have PD-1 expression testing for enrollment on the study. All sites of disease that are amenable to biopsy are allowable per protocol. Measurable lesions that are the only site of measurability per RECIST v1.1 cannot be biopsied due to obstruction of measurement. Additionally, previously irradiated lesions cannot be biopsied due to potential for necrotic and nonviable tissue.

Standard techniques will be used for all biopsies, which may include CT, ultrasound, or endoscope depending on site of biopsiable lesion. The sample should be obtained as core or endoscopic. Fine needle aspirations (FNA) samples are acceptable. The total number of core biopsies obtained should be approximately 6-15, with an average of 10.

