### **3.2. Inclusion Criteria**

In order to be eligible for participation in this study, the subject must meet all of the following:

- 3.2.1. Age  $\geq$  18 years of age on day of signing informed consent.
- 3.2.2. Be willing and able to provide written informed consent/assent for the study
- 3.2.3. Histologically or cytologically confirmed adenocarcinoma of the distal esophagus, gastroesophageal junction or stomach, including patients with HER2+ disease. Distal esophagus is defined as within 5 centimeters of the GEJ.
- 3.2.4. Patients must have metastatic or unresectable disease, including those with HER2+ disease.
- 3.2.5. Must have progressed on at least one line of prior therapy for metastatic disease, or be intolerant to that therapy if they have not progressed, and for HER2+ disease should have received prior trastuzumab.
- 3.2.6. Life expectancy  $\geq$  12 weeks
- 3.2.7. Have a performance status of 0 or 1 on the ECOG Performance Scale.
- 3.2.8. Have measurable disease per RECIST v1.1, assessed within 4 weeks prior to study entry.
- 3.2.9. Tumor deemed amenable to biopsy by core for metastatic site or endoscopic biopsy for primary tumor (for both before and on-treatment biopsies).
- 3.2.10. Patient must be willing to undergo two biopsies - before and on-treatment, provided the procedure is not deemed high-risk and is clinically feasible.
- 3.2.11. Demonstrate adequate organ function as defined in **Table 1**, all screening labs should be performed within 7 days of treatment initiation.

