### **8.2. Tissue Samples**

Pre-treatment and on-treatment biopsies are to be collected on patients when safe and feasible.

Details and methods for obtaining, processing, and shipping the fresh tumor biopsy are as follows:

- 6-15 (average 10) core biopsies measuring at least 4mm, if possible 10mm will be obtained from an accessible and safe primary or metastatic tumor site
- When feasible, all core samples should be obtained from the same lesion/location at the appropriate time point
- When feasible, 16-18 gauge needles should be used to obtain core samples. FNA samples are acceptable
- Samples should contain at minimum 20% tumor viability as measured by adequate number of living cells based on H&E slide
- Specimens will be collected/stored in FFPE or as a single cell suspension via the Correlatives Sciences Unit SOP.

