13 Tumor molecular profiling can be performed on archived tissue or newly obtained during the study participation

14 If a coumadin-based anticoagulant is given, INR should be monitored weekly for the first 4 weeks after initiation of therapy and again upon discontinuing epacadostat.

15 TSH required at all day 1 visits, T3 and fT4 only required if TSH is abnormal or patient is symptomatic.

16 For women of childbearing potential, a serum pregnancy test is required at screening but must be within 3 days before first dose of study treatment. Pregnancy tests (serum or urine) should be repeated as needed if required by institutional regulations.

17 CEA and CA19-9 will be checked at baseline on C1D1 prior to Pembrolizumab and Epacadostat and, if elevated, followed every 9 weeks during therapy.

18 Before pembrolizumab dose every 3 weeks

19 Fresh tumor biopsy will be collected pre-treatment (between day -14 to day 0) and on treatment (day 42 ± 5 days). For additional reference go to section 4.9.3 and 8.2

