#### 10.2.2. **Index and Non-Index Lesions**

All measurable lesions, up to a maximum of five lesions per organ and ten lesions in total, should be identified as index lesions to be measured and recorded in the medical record at Screening. The index lesions should be representative of all involved organs. In addition, index lesions should be selected based on their size (lesions with the longest diameters), their suitability for accurate repeat assessment by imaging techniques, and how representative they are of the patient's tumor burden. At screening, a sum of the products of diameters (SPD) for all index lesions will be calculated and considered the baseline sum of the products of diameters. Response criteria to be followed are listed below. The baseline sum will be used as the reference point to determine the objective tumor response of the index lesions at tumor assessment.

Measurable lesions, other than index lesions, and all sites of non-measurable disease, will be identified as non-index lesions. Non-index lesions will be recorded in the medical record and should be evaluated at the same assessment time points as the index lesions. In subsequent assessments, non-index lesions will be recorded as "stable or decreased disease," "absent," or "progression."

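### A measurable lesion biopsied twice can stay in the tumor sum although 4.9.3 says biopsy obstructs measurement, and the entry criteria do not carry the 4.9.3 bar

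*Combined protocol and SAP*

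**What the plan says.** Section 4.9.3 states that fresh biopsies "will be required at baseline and on treatment of the same lesion", the second at day 42 ± 5. On quantity it says: "The total number of core biopsies obtained should be approximately 6-15, with an average of 10". On site it first says "All sites of disease that are amenable to biopsy are allowable per protocol" and then restricts this: "Measurable lesions that are the only site of measurability per RECIST v1.1 cannot be biopsied due to obstruction of measurement". It also bars biopsy of previously irradiated lesions.

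Section 10.2.2 sets the rule for the tumor sum: "All measurable lesions, up to a maximum of five lesions per organ and ten lesions in total, should be identified as index lesions". It makes no exception for a biopsied lesion. Progression for the primary endpoint is by RECIST v1.1 (12.2.1), and the plan gives no separate rule for choosing RECIST target lesions.

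For entry, 3.2.8 asks for measurable disease without a minimum number of lesions. 3.2.9 asks for: "Tumor deemed amenable to biopsy by core for metastatic site or endoscopic biopsy for primary tumor". 3.2.10 asks for willingness to have two biopsies, subject to risk and feasibility. Appendix A items 8 to 10 repeat these three criteria.

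**The concern.** The plan gives a measurement reason for sparing a lesion and then applies it in one situation only. If biopsy impairs measurement of a sole lesion, it impairs measurement of a lesion that has companions too; the companions only dilute the error. Yet the diluted case enters the sum without a flag. Response and progression could then partly reflect the procedure. In a trial of 30 patients judged on a count, one or two misread patients are not negligible.

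The second strand concerns entry. The 4.9.3 bar appears in neither the inclusion criteria nor the checklist. A patient can therefore be enrolled correctly into a study whose title and synopsis call for paired biopsies, and then have no site that 4.9.3 permits.

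**Working it through.** **1. The plan's own figure.** Inputs from 12.1: N = 30, null 20%, alternative 39%, one-sided 10%, exact binomial, stated power 80%. The smallest r with P(X ≥ r | 0.20) ≤ 0.10 is r = 10, which gives 0.061 (r = 9 gives 0.129). Power is P(X ≥ 10 | 0.39) = 0.793. The stated 80% reproduces, and this point does not alter it.

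**2. The rules side by side.**
- One measurable lesion: 4.9.3 forbids its biopsy, so the sum is protected.
- Two or more measurable lesions, a measurable one biopsied, within five per organ and ten in total: 4.9.3 permits the biopsy and 10.2.2 makes the lesion an index lesion. Nothing excludes or flags it.
- A non-measurable lesion biopsied, such as a primary sampled by endoscopy: non-index under 10.2.2, so no problem arises.

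**3. Timing.** The baseline scan may be up to 28 days before first dose (4.9.2). The first biopsy is at day -14 to 0 (Section 9, footnote 19), and its order relative to the scan is not stated. The second biopsy is at day 37 to 47. The first on-study scan is at 63 ± 5 days (10.1), that is day 58 to 68. The gap runs from 58 - 47 = 11 to 68 - 37 = 31 days. With the ± 7 days of 4.9.2 it is 9 to 33 days. Both biopsies can therefore lie between baseline and first assessment.

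**4. Enlargement needed to trigger progression.** Assume m equal index lesions of which only the biopsied one changes. The 20% rise in the sum of products in 10.2.3 needs a product rise of 20% × m in that lesion, or √(1 + 0.2m) - 1 in each diameter:

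| m | rise in each diameter |
|---|---|
| 2 | 18% |
| 3 | 26% |
| 5 | 41% |
| 10 | 73% |

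For a 10 mm lesion and m = 2, 18% is 1.8 mm per axis. 10.2.3 adds a 5 mm absolute increase. If that is read on a sum of diameters, the same lesion would have to grow from 10 to 15 mm.

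**5. Shrinkage from tissue removal.** Assume a spherical lesion of diameter D and n cores of diameter d and length L. The fraction removed is (π/4·d²·L·n)/(π/6·D³) = 1.5·d²·L·n/D³. From 8.2: n = 6 to 15 and L at least 4 mm. Core diameter in millimetres is not given (8.2 gives a needle gauge); d = 1.0 to 1.2 mm is assumed.
- D = 10, L = 4: 1.5 × 1.0 × 4 × 6/1000 = 3.6% to 1.5 × 1.44 × 4 × 15/1000 = 13.0% of volume per round. With (1 - f)^(1/3) - 1, that is 1.2% to 4.5% of diameter.
- D = 20, at the upper end (L = 10, n = 15, d = 1.2): 1.5 × 1.44 × 10 × 15/8000 = 4.1% of volume, 1.4% of diameter.

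Two rounds at the 4.5% figure on one of two equal 10 mm lesions lower the sum of diameters by (1 - 0.955²)/2 = 4.4%. The partial-response threshold in 10.2.3 is 30%. Bleeding or inflammation would act the other way by an unknown amount.

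**6. Sensitivity of the test, as illustration only.** Suppose a fraction f of truly progression-free patients were read as progressed, so that p = 0.39(1 - f). For f = 3%, 5% and 10%, power falls from 79.3% to 75.4%, 72.5% and 64.7%. With 0.39 × 30 = 11.7 such patients expected, these fractions are about 0.35, 0.6 and 1.2 patients. No f can be derived from the documents.

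**7. The entry path.** Take a patient with one measurable lesion and no other biopsiable site. 3.2.8, 3.2.9 and 3.2.10 are met, as are checklist items 8 to 10; 4.9.3 forbids the biopsy. The same holds if the only accessible site has been irradiated. The qualifiers in 3.2.10 and 8.2 concern risk, safety and feasibility; the sole-lesion bar concerns measurement.

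**The case against.** The strongest reply is that 4.9.3 makes a coherent threshold choice: protect the lesion that nothing can replace, and tolerate some error where others share the sum. Several provisions also limit the damage. Progression in clinically stable patients is re-imaged at least 4 weeks later (4.9.2, 10.3), progression needs a 5 mm absolute increase, and unconfirmed responses are scored as stable disease (10.2.3). 10.2.2 lists how reliably a lesion can be re-measured on imaging among its selection factors, which a site could use to leave out a biopsied lesion. Finally, 10.2.2 is an irRC-type rule based on products, whereas primary PFS is by RECIST v1.1.

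Much of this stands. The safeguards reduce false progression from transient swelling. They do not act on a lasting loss of tissue, which can lower both the sum and the nadir. The selection factor sits beside an instruction to take all measurable lesions up to the cap and does not mention biopsy, so two sites could apply it differently. The irRC point means that 10.2.2 does not itself fix what enters the RECIST sum; but no RECIST rule excludes the biopsied lesion either.

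On entry, the reply is that paired tissue serves an exploratory objective (1.3.1), samples are only collected and stored (Section 8), and 8.2 collects them when safe and feasible. That is right, and it limits the consequence to inconsistent passages.

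A reader might also infer more than the documents support:
- That most patients are affected. The share is P(biopsied lesion measurable) × P(within cap), and neither is given. With assumed values of 0.2 to 1.0 and 0.8 to 1.0 it runs from 16% to 100%.
- That the bias has a known direction. 4.9.3 names obstruction and no sign.
- That 9% to 32% of a 10 mm lesion is removed per round. This needs every core to run the full 10 mm inside a 10 mm sphere, which only a path through the centre can do. Fine needle aspirates, which are accepted, do not fit the core model.
- That a particular number of patients, such as 3 to 6 of 30, would have no permitted site. That needs an assumed share of 10% to 20%, for which the documents give no basis.

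**Conclusion.** The point holds within limits. In any patient with two or more measurable lesions whose biopsied lesion is measurable and within the index cap, 10.2.2 keeps in the sum a lesion that the plan's own reasoning treats as compromised, and nothing keeps it out of the RECIST v1.1 sum for the primary endpoint. The effect is of unknown size and sign. On the assumptions above it is well short of response thresholds and probably small except for lesions near 10 mm with few companions. An effect on 6-month PFS is plausible, but the text does not establish one, and the stated power is untouched. The change is worth making because it is cheap.

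The entry gap is a plain inconsistency and needs no assumed figure. How many patients it would touch is not in the documents.

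**What to change.** Add one sentence to 10.2.2, worded for both irRC index lesions and RECIST v1.1 target lesions: the lesion selected for biopsy is recorded as non-index/non-target at baseline whenever another measurable lesion exists. It is still followed as non-index disease. The cost is one fewer index or target lesion in some patients, and possibly one organ less represented, so the sentence should say that it takes precedence over the aim in 10.2.2 of representing all involved organs.

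Separately, reconcile 3.2.9 and checklist item 9 with 4.9.3, for both the sole-measurable-lesion bar and the irradiated-lesion bar, so that the passages agree on what happens to a patient with no permitted biopsy site. Which way to resolve this is for the sponsor and investigator. The cost is a wording change and, if the bar moves into eligibility, some screen failures whose number cannot be estimated from the documents.

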#### 4.9.4. **Performance and Quality of Life Assessments**

##### 4.9.4.1. **Eastern Cooperative Oncology Group Performance Status**

The investigator or qualified designee will assess ECOG performance status (Appendix C) at screening, prior to the administration of each dose of study treatment and discontinuation of study treatment as specified in the schedule of events calendar (Section 9).

#### 4.10. **General Concomitant Medication and Supportive Care Guidelines**

Medications or vaccinations specifically prohibited in the exclusion criteria are not allowed during the study. If there is a clinical indication for one of these or other medications or vaccinations specifically prohibited during the study, discontinuation from study therapy may be required. The investigator should discuss any questions regarding this with the Merck and Incyte clinical team. The final decision on any supportive therapy rests with the principal investigator and/or the subject's primary treating physician. However, the decision to continue the subject on study therapy schedule requires the mutual agreement of the investigator, Merck and Incyte, and the subject.

##### 4.10.1. **Acceptable Concomitant Medications**

All treatments that the investigator considers necessary for a subject's welfare may be administered at the discretion of the investigator in keeping with the community standards of medical care. All concomitant medication will be recorded on the eCRF, including all prescription, over-the-counter (OTC), herbal supplements, and IV medications and fluids. If changes occur during the study period, documentation of drug dosage, frequency, route, and date may also be included on the CRF.

All concomitant medications received within 28 days before the first dose of study treatment and 30 days after the last dose of study treatment should be recorded. Concomitant medications administered for 30 days after the last dose of study treatment should be recorded for SAEs. Bone protectants (bisphosphonates and denosumab) are allowed for treatment of bone metastases while patients are on the study.

#### 4.10.2. **Restricted Medications**

Low-dose Coumadin (1 mg) is acceptable; however, standard dose levels of Coumadin are prohibited given fluctuations in INR.

#### 4.10.3. **Prohibited Medications**

Subjects are prohibited from receiving the following therapies during the screening and treatment phase (including retreatment for post-complete response relapse) of this study:

- Antineoplastic systemic chemotherapy or biological therapy
- Any immunological-based treatment for any reason
- Investigational medications other than pembrolizumab or epacadostat
- Radiation therapy
  - Note: Palliative radiation therapy to a symptomatic solitary lesion or to the brain may be allowed at the investigator’s discretion.
- Live vaccines within 30 days prior to the first dose of study treatment and while participating in the study. Examples of live vaccines include, but are not limited to, the following: measles, mumps, rubella, varicella/zoster, yellow fever, rabies, BCG, and typhoid vaccine.
- Systemic glucocorticoids for any purpose other than to modulate symptoms from an event of clinical interest of suspected immunologic etiology.
- Any melatonin supplements.
- Any MAOI or drug associated with significant MAO inhibitory activity agents is prohibited from 21 days before Day 1 through 2 weeks after the final dose of INCB024360 has been taken (see 14.3).
- Any UGT1A9 inhibitor, including: acitretin, amitriptyline, androsterone, cyclosporine, dasatinib, diclofenac, diflunisal, efavirenz, erlotinib, estradiol (17-beta), flutamide, gefitinib, gemfibrozil, glycyrrhetic acid glycyrrhizin, imatinib, imipramine, ketoconazole, linoleic acid, mefenamic acid, mycophenolic acid,

niflumic acid, nilotinib, phenobarbital, phenylbutazone, phenytoin, probenecid, propofol, quinidine, ritonavir, Sorafenib, sulfapyrazone, valproic acid, and verapamil.

Subjects who, in the assessment by the investigator, require the use of any of the aforementioned treatments for clinical management should be removed from the study. Subjects may receive other medications that the investigator deems to be medically necessary.

The exclusion criteria (Section 3.3) describes other medications that are prohibited during this study. There are no prohibited therapies during the post-treatment follow-up phase.

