- 3.3.10. Has known active central nervous system (CNS) metastases and/or carcinomatous meningitis. Subjects with previously treated brain metastases may participate provided they are stable (without evidence of progression by imaging for at least four weeks prior to the first dose of study treatment and any neurologic symptoms have returned to baseline), have no evidence of new or enlarging brain metastases, and are not using steroids for at least 7 days prior to study treatment. This exception does not include carcinomatous meningitis which is excluded regardless of clinical stability. Patient with prior CNS metastases treated w/ prior RT will also need all of the following: A. 2 months off RT before starting study or 4 weeks following XRT if MRI is stable and the patient is off steroids, B. Baseline MRI with no edema, and C. stable for at least 8 weeks.
- 3.3.11. Has known additional malignancy that has progressed or requires active treatment. Exceptions include basal cell carcinoma of the skin, squamous cell

- carcinoma of the skin, or in situ cervical cancer that has undergone potentially curative therapy.
- 3.3.12. Has active infection requiring systemic therapy
- 3.3.13. Has a known history of active TB (Bacillus Tuberculosis)
- 3.3.14. Has known active Hepatitis B (e.g., HBsAg reactive) or Hepatitis C (e.g., HCV RNA [qualitative] detected)
- 3.3.15. Has a diagnosis of immunodeficiency or is receiving systemic steroid therapy or any other form of immunosuppressive therapy within 7 days prior to the first dose of study medication
- 3.3.16. Has a known history of Human Immunodeficiency Virus (HIV) (HIV 1/2 antibodies)
- 3.3.17. Is pregnant or breastfeeding, or expecting to conceive or father children within the projected duration of the study, starting with pre-screening or screening visit through 120 days after the last dose of study treatment
- 3.3.18. Has had monoamine oxidase inhibitors within 21 days before screening
- 3.3.19. Has any history of serotonin syndrome after receiving 1 or more serotonergic drugs
- 3.3.20. Has presence of a gastrointestinal condition that may affect drug absorption
- 3.3.21. Use of systemic corticosteroids
- 3.3.22. Has history or presence of an abnormal electrocardiogram (ECG) which, in the investigator's opinion, is clinically significant.
- QTcF > 480 ms or presence of a Left Bundle Branch Block (LBBB). If the QRS duration > 120ms, the JTc can be used in place of the QTcF. The JTc must be < 340 ms.

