#### **4.2. Duration of Treatment and Subject Participation**

Each subject enrolled in the study will continue receiving combination study treatment in continuous 21-day cycles for up to 24 months, and then treatment with monotherapy epacadostat may continue as long as the subject is receiving benefit from treatment and has not had disease progression or met any criteria for study withdrawal. If the subject discontinues all study treatment, the treatment phase will end, and the subject will enter the follow-up phase. Study participation is expected to average about 6 months.

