## 14.2. **APPENDIX B: INFORMATION REGARDING EFFECTIVENESS OF CONTRACEPTIVE METHODS**

### **For Subjects Participating in the Study:**

The following methods have been determined to be more than 99% effective (< 1% failure rate per year when used consistently and correctly and are permitted under this Protocol for use by the subject and his/her partner:

- Complete abstinence from sexual intercourse
- Double barrier methods:
  - Condom with spermicide in conjunction with use of an intrauterine device
  - Condom with spermicide in conjunction with use of a diaphragm
- Birth control patch or vaginal ring
- Oral, injectable, or implanted contraceptives
- Surgical sterilization (tubal ligation or vasectomy)

14.3. **APPENDIX C: EASTERN COOPERATIVE ONCOLOGY GROUP (ECOG) PERFORMANCE STATUS**

Grade	Description
0	Normal activity. Fully active, able to carry on all pre-disease performance without restriction.
1	Symptoms, but ambulatory. Restricted in physically strenuous activity, but ambulatory and able to carry out work of a light or sedentary nature (e.g., light housework, office work).
2	In bed <50% of the time. Ambulatory and capable of all self-care, but unable to carry out any work activities. Up and about more than 50% of waking hours.
3	In bed >50% of the time. Capable of only limited self-care, confined to bed or chair more than 50% of waking hours.
4	100% bedridden. Completely disabled. Cannot carry on any self-care. Totally confined to bed or chair.
5	Dead.

\*As published in Am. J. Clin. Oncol.: *Oken, M.M., Creech, R.H., Tormey, D.C., Horton, J., Davis, T.E., McFadden, E.T., Carbone, P.P.: Toxicity And Response Criteria Of The Eastern Cooperative Oncology Group. Am J Clin Oncol 5:649-655, 1982. The Eastern Cooperative Oncology Group, Robert Comis M.D., Group Chair.*

14.4. **APPENDIX D: PROHIBITED MONOAMINE OXIDASE INHIBITORS AND DRUGS ASSOCIATED WITH SIGNIFICANT MONOAMINE OXIDASE INHIBITORY ACTIVITY**

Monoamine Oxidase Inhibitors	Drugs Associated With Significant Monoamine Oxidase Inhibitory Activity	UGT1A9 inhibitor

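### Section 4.10.3 bans MAO inhibitors until 2 weeks after the last epacadostat dose yet says nothing is prohibited after treatment, and the eligibility checklist covers fewer drugs than the ban

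*Combined protocol and SAP*

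**What the plan says.** Four parts of the protocol govern these drugs after the last dose.

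- **4.10.3, MAO-inhibitor bullet.** Use of MAO inhibitors and of drugs with significant MAO-inhibitory activity "is prohibited from 21 days before Day 1 through 2 weeks after the final dose of INCB024360 has been taken (see 14.3").
- **4.10.3, lead-in to the list.** The prohibitions hold "during the screening and treatment phase (including retreatment for post-complete response relapse) of this study".
- **4.10.3, last sentence.** "There are no prohibited therapies during the post-treatment follow-up phase".
- **6.4.** MAO inhibitors, meperidine (under its brand name), linezolid and methylene blue are said to be prohibited for the study, with no end date.

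Section 4.2 fixes when the phases change: "If the subject discontinues all study treatment, the treatment phase will end, and the subject will enter the follow-up phase".

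At entry, exclusion 3.3.18, repeated in the Appendix A checklist, reads "Has had monoamine oxidase inhibitors within 21 days before screening". It does not mention other drugs with MAO-inhibitory activity.

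The bullet's cross-reference leads to section 14.3, which is "APPENDIX C: EASTERN COOPERATIVE ONCOLOGY GROUP (ECOG) PERFORMANCE STATUS". The drug list is in 14.4, "APPENDIX D: PROHIBITED MONOAMINE OXIDASE INHIBITORS AND DRUGS ASSOCIATED WITH SIGNIFICANT MONOAMINE OXIDASE INHIBITORY ACTIVITY".

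**The concern.** A physician or coordinator looking after a patient who has just stopped epacadostat can find two opposite answers in one section: the bullet still forbids these drugs for 2 weeks, and the closing sentence says nothing is forbidden. Section 4.10.3 also says that a subject who needs a listed treatment should come off the study. If such a subject is then regarded as being in follow-up, the closing sentence allows the drug at once while the bullet does not. Those subjects are the ones most likely to be given it.

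The stake is patient safety, not the efficacy analysis. Section 6.4 singles out these agents as the ones most linked to serotonin syndrome, and the review reproduced in Appendix E describes the syndrome as possibly fatal. Section 6.4 also calls the chance that epacadostat contributes theoretical, so the stake should not be overstated.

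The second issue arises at entry. Staff are directed to Appendix A when they enrol, and it names a narrower set of drugs than 4.10.3 prohibits.

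**Working it through.** There is no planned figure to reproduce. The check is a comparison of texts with day counts.

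**1. After the last dose.** Inputs: the ban lasts 14 days after the last epacadostat dose (4.10.3), and follow-up begins on stopping all study treatment (4.2). Let follow-up begin *f* days after the last epacadostat dose.

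Days of the ban inside follow-up = max(0, 14 − *f*).

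| Reading | *f* | Overlap |
|---|---|---|
| 4.2, with epacadostat the last drug taken | 0 | 14 of 14 days |
| Follow-up starts only after the safety visit at about 30 days | 30 | max(0, 14 − 30) = 0 days |

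The first row is realistic. Epacadostat is taken daily against pembrolizumab every 3 weeks, and 4.2 and 4.4 allow epacadostat alone beyond 24 months. If treatment as a whole ends some days after the last epacadostat dose, the overlap shrinks day for day.

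The second row is harder to hold, because section 4.6 places the 30-day safety visit inside the Follow-Up Phase. It also removes only the conflict with the closing sentence. The section 9 calendar shows end of treatment in a column separate from the Treatment Phase, so on that layout the 2 weeks after the last dose still lie outside the period named in the lead-in.

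**2. Washout anchors at entry.** Inputs: 21 days before screening (3.3.18), 21 days before Day 1 (4.10.3), and screening of up to 28 days (4.3.1). Let screening start *s* days before Day 1, with *s* from 1 to 28.

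- 3.3.18 reaches back to day −(*s* + 21): day −22 for *s* = 1 and day −49 for *s* = 28.
- 4.10.3 reaches back to day −21.
- Difference = (*s* + 21) − 21 = *s*, that is 1 to 28 days, with 3.3.18 always the earlier.

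A subject free of MAO inhibitors from 21 days before screening through Day 1 meets both rules. The anchors differ but do not conflict.

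**3. Drug scope.**

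| Place | MAO inhibitors | Meperidine, linezolid, methylene blue |
|---|---|---|
| 3.3.18 and Appendix A | named | not named |
| 4.10.3 bullet, with list in 14.4 | covered | covered (second column of 14.4) |
| 6.4 | named | named |

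Appendix E describes linezolid as an MAO inhibitor, so 3.3.18 could be read to include it, although 14.4 lists it in a separate column. Meperidine and methylene blue are named in no exclusion criterion.

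**The case against.** The strongest reply is that the protocol separates end of treatment from follow-up. The section 9 calendar gives end of treatment its own column before the Post-Treatment columns. Section 4.5 sets the end-of-treatment visit about 30 days after the last dose and sends patients with a complete response to the safety visit first and the Follow-Up Period afterwards. On that reading the 2-week ban expires before the closing sentence applies. The reading is possible, but it fits 4.2 and 4.6 less well and leaves the lead-in unexplained.

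Several stronger readings are tempting, and the documents do not support them.

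- *That the serotonin-syndrome safeguard fails when patients stop.* The bullet names the drug class and an end date, and 6.4 also prohibits these agents. The rule is contradicted, not missing.
- *That the two anchors leave a washout gap.* For MAO inhibitors, 3.3.18 is the longer lookback, and 4.10.3 covers screening itself.
- *That the wrong pointer hides the list.* It is a clerical slip. Appendix D is clearly titled, and 6.4 names the key agents.
- *That a patient recently given linezolid or meperidine would pass unnoticed at entry.* Section 4.3.5 requires review of washouts and a record of medication in the 28 days before starting, which spans the 21-day window. Criterion 3.3.12 excludes active infection under systemic therapy, and 3.3.23 gives the investigator general discretion. What remains is only that the checklist names fewer drugs.
- *That all 30 patients are affected, and again after a second course.* Thirty is an upper bound on those who reach the window. Patients who die on treatment never do, and a second course is open only to the few who meet the section 4.8 conditions. The documents give no estimate of how many would need one of these drugs within 14 days.

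**Conclusion.** The contradiction within section 4.10.3 is real and should be corrected. Its size is up to 14 of 14 days of the ban, assuming that epacadostat is the last drug taken and that follow-up starts as 4.2 states. The count against the closing sentence falls to 0 only if follow-up is taken to begin after the safety visit at about 30 days. Section 6.4 adds a third wording without an end date. The rule after the last dose is therefore ambiguous, for a risk the protocol itself calls theoretical.

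At entry, the anchors differ by 1 to 28 days and are compatible, but the drug scope of 3.3.18 and Appendix A is narrower than that of 4.10.3. The pointer to 14.3 is clerical. No endpoint, sample size or efficacy analysis depends on any of this.

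**What to change.** - Reconcile the lead-in and closing sentence of 4.10.3 with the MAO-inhibitor bullet and with 6.4, so that all state one period and say how it relates to the end-of-treatment and follow-up phases of 4.2, 4.6 and section 9.
- Use one washout anchor and one drug scope in 3.3.18, 4.10.3 and the Appendix A checklist.
- Change the cross-reference in 4.10.3 from 14.3 to 14.4.

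The investigator and the two supplying companies decide which window and which drug list apply; this review takes no position on either. The cost is protocol and checklist wording, with no change to the statistical design.
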